## **Other Outcome Measures**

- Illegal flavored products being sold: The simulated buyer will report if the seller mentions that flavored (non-national-standard) e-cigarette products are available in the stores.
- Online contact: The simulated buyer will report if WeChat account information is publicly displayed for adding contacts.
- Delivery service offered: The simulated buyer will report if the seller mentions that products ordered online can be delivered.
- Marketing claims: The simulated buyer will record the marketing claims made by the seller to promote the products

### **2.2.2. Covariates**

The assessment tool should be designed primarily based on the Vape Shops Standardized Tobacco Assessment for Retail Setting (V-STARS) and the Tobacco Advertising, Promotion and Sponsorship (TAPS) bans compliance guide, as well as published articles. It will be further adapted by investigators who are familiar with Chinese e-cigarette retailers and laws and have observed store characteristics, to the Chinese context to collect information mainly on store internal/external environmental features (e.g., location, advertising, warning signs, and licensing), product availability, and seller behaviors. Detailed information on covariates is listed as below:

- Buyer characteristics: Sex, Age
- Seller characteristics: Sex, Age perceived by the simulated buyers (18-29, 30-40, >40 years old)
- Store characteristics: Store location (In mall, on street), region, age-of-sale warning sign presented, license to sell e-cigarettes presented, health warning presented, and advertising.

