5.1. Treatment and control

Each e-cigarette store will be visited by a simulated buyer (also serving the role of a data collector) who aged 18-19 years old and wear a certain type of attire, including carried accessories. If necessary, the buyers will claim that (1) they are adults but will not show any age proof; (2) they have never tried any tobacco products; (3) they want to buy e-cigarettes out of curiosity because their friends are using the products.

The sellers' behaviors and claims will be documented immediately after the simulated buyers leave the stores. The primary difference between the treatment group and control group is the attire that buyers wear: school uniforms vs. casual attire.

Treatment group: The e-cigarette stores will receive a simulated buyer of a randomly assigned sex who will wear a school uniform, carry a school bag, and attempt to purchase e-cigarette products.

Control group: The e-cigarette stores will receive a simulated buyer of a randomly assigned sex who will wear casual attire, carry a business style bag (backpacks for males and handbags for females), and attempt to purchase e-cigarette products.

1:1 matching: After mystery shopping and point-of-sale auditing in an e-cigarette store, simulated buyers will search for the nearest store where traditional cigarettes can be purchased and conduct a similar visit intervention.

Note: The simulated adolescent buyer (also the data collector) will role-play a minor under 18 years old who attempt to buy e-cigarettes. Only adolescents aged 18 or 19 years old will be recruited in this study because it is theoretically difficult to distinguish whether they are under or above 18 years old from the facial features. This trial will not recruit minors who are younger than 18 years old because it is illegal for them to purchase e-cigarette products in China.

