8.1. General statistical methods

Summary statistics will be presented for both the treatment and control groups. Continuous variables will be summarized by the number of observations, mean, standard deviation, median, minimum, and maximum. Categorical variables will be summarized using frequency counts and percentages. Descriptive analyses of the distributions of the e-cigarette seller behavior outcomes between two types of attire (treatment and control groups), including successful purchases, inquiring about buyer age, requesting ID cards for age verification, and dissuading buyers from use, as well as store environment features, and sellers' demographic characteristics, will be conducted with t-tests and chi-square tests detecting statistically significant differences.

The significance level for comparisons between the two groups is set at $\alpha=0.05$ (two-sided). Differences between the study groups will be considered statistically significant if the p-value is less than 0.05. All analyses will be performed using Stata MP 17.

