No, the e-cigarette store is not open (please skip to the end of the questionnaire and submit your answer sheet)

No, the seller is not in the store (please skip to the end of the questionnaire and submit your answer)

No, other _____ * (please skip to the end of the questionnaire and submit your answer sheet)

15. Is the tobacco retail license visible [Single choice question] *

Yes

No

16. Is there a "No use by minors" slogan in the store (excluding slogans on product packaging) [Single-choice question] *

Yes

No

17. Are there any of the following health warning signs in the store (excluding slogans on product packaging) [Single choice question] *

Yes, there is a "Smoking is harmful to health" sign

Yes, there is a "E-cigarettes are harmful to health" sign

Yes, both of the above exist

No

18. Are there children's toys, car models, figurines, and/or other decorations placed on the shelves or counters? [Note that these decorations need to be targeted at teenagers.] [Single Choice Question] *

Yes, specifically _____ *

No

19. Gender of the seller: (When there are multiple sellers, this question refers to the seller who communicates with the simulated buyer the most. The same applies to the questions below.)

Male

Female

20. Age of the seller (the simulated buyer needs to estimate) [Single-choice question] *

18-24 years old

25-29 years old

30-39 years old

>40 years old

21. Did the seller ask the simulated buyer if he or she was an adult? [Single Choice Question] * -----Questions such as "Are you an adult?" "Are you over 18?" "How old are you?" "Are you a student?" etc.

Yes

No

22. Did the seller ask to see the simulated buyer's ID? (If the seller requires you to fill in identity information on the system, please select Yes.) [Single Choice Question] *

Yes

No

23. Did the seller ask the simulated buyer to leave? (No sales communication) [Single Choice Question] * ----- If the seller does not check the age until the simulated buyer pays, the sales communication has been completed at this point. In this case, you should select "No" and continue to fill in the questionnaire.

○No

- Yes, the seller asked you (the simulated buyer) to leave without asking about their age. (Please skip to the end of the questionnaire and submit your answer.)
- Yes, the seller asked you (the simulated buyer) to leave after asking their age. (Please skip to the end of the questionnaire and submit your answer.)

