### **1.1.3. Blinding**

It will be impossible to blind study subjects (e-cigarette stores) regarding the assignment to the intervention or control group, as letting sellers in the e-cigarette stores see the buyers' attire is part of the treatment. However, sellers will not be aware of their participation in this trial due to the mystery shopping approach adopted.

The trial team, consisting of both simulated buyers and coordinators, will also not be blinded to the e-cigarette stores in the intervention and control groups, as there is no way to prevent them from knowing which e-cigarette stores have simulated buyers wearing school uniforms or casual attire on each day.

The statistician conducting the analyses will have no direct contact with the e-cigarette stores but will not be blinded to the treatment allocation.

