### 2.3.2. Analysis of Primary Outcome

For the primary outcome, successful purchase rates will be analyzed using Chi-square tests to determine if the differences between the treatment group and the control group are statistically significant. Multivariate logistic regression models will be further employed to analyze the treatment effect, adjusting for covariates.

A national map depicting the geographic variations in the outcomes of successful purchase rates will be created using the R package DrawChinaMap.

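### In stores with more than one seller, the supporting adjusted models condition on who served the buyer, which is settled only after the attire is seen

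*SAP*

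**What the plan says.** - **Covariates.** SAP 2.2.2 lists buyer, seller and store characteristics. The seller entry is "Seller characteristics: Sex, Age perceived by the simulated buyers (18-29, 30-40, >40 years old").
- **Models.** SAP 2.3.2 first states that "For the primary outcome, successful purchase rates will be analyzed using Chi-square tests". It then adds: "Multivariate logistic regression models will be further employed to analyze the treatment effect, adjusting for covariates". No subset of the list is named. SAP 2.3.3 and 2.3.4 plan adjusted logistic models for the secondary and other outcomes in the same way.
- **Which seller is recorded.** Item 19 of the assessing tool (Protocol Appendix 4) instructs: "When there are multiple sellers, this question refers to the seller who communicates with the simulated buyer the most". The same rule applies to the items that follow.
- **How age is obtained.** Item 20 reads "Age of the seller (the simulated buyer needs to estimate"). Under SAP 1.1.3 the buyers are not blinded to arm.
- **Order of events.** SAP 1.1.3 says that "letting sellers in the e-cigarette stores see the buyers' attire is part of the treatment". Protocol 5.1 says the sellers' "behaviors and claims will be documented immediately after the simulated buyers leave the stores", and Protocol 5.2 places the record of seller demographics in the same post-visit step.
- **Descriptive comparison.** SAP 2.3.1 already compares sellers' demographic characteristics between the arms.

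Neither document says how many stores have more than one seller, whether attire influences who serves, or which result prevails if the chi-square test and the logistic model differ.

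**The concern.** The primary objective is the effect of attire on what sellers do. One way a uniform could act is by changing who deals with the buyer: a junior assistant might hand over to an older colleague or the owner. That handover is part of the effect of the randomised attire. A model that holds the serving seller's age and sex constant compares uniform and casual visits as if the handover had not happened, so it no longer targets the full randomised contrast.

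Guessed age adds a second, weaker route. The buyer knows the arm and, by the time of data entry, the outcome. Protocol 8.7 expects some buyers to be asked to leave as soon as they enter. If that is more common in uniform, the guess rests on a shorter encounter in that arm, and its error can depend on arm and outcome.

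At stake is the covariate-adjusted effect estimate for each outcome, since the adjusted models are the only planned source of one.

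**Working it through.** The plan gives no figure on this point to reproduce. The purchase rates are left to the pilot, and the share of multi-seller stores is not stated. The calculation below therefore shows how the size depends on assumptions; it does not estimate the size.

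**Setup (all values assumed).** Let U = 1 for uniform and S = 1 for an older, stricter seller, with logit P(sale) = 1.0 − 0.8·U − 1.5·S. The sale probabilities are:
- casual, younger seller 0.7311; casual, older seller 0.3775
- uniform, younger seller 0.5498; uniform, older seller 0.2142

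Older sellers serve 40% of casual visits, so q_C = 0.40. In the uniform arm q_U = 0.40 + f·d, where f is the share of multi-seller stores and d is the shift in who serves there.

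**Formulas.**
- Total effect = [q_U·0.2142 + (1 − q_U)·0.5498] − [0.40·0.3775 + 0.60·0.7311]. The second bracket is 0.590.
- Seller-adjusted effect, standardised to the pooled seller mix q = (q_C + q_U)/2: q·(0.2142 − 0.3775) + (1 − q)·(0.5498 − 0.7311).
- The two differ in size by f·d times the mean seller gap, [(0.7311 − 0.3775) + (0.5498 − 0.2142)]/2 = 0.3446.

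**Results** (percentage points, from unrounded values):

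| Multi-seller stores | Older seller serves there, uniform v casual | q_U | Total | Adjusted | Change in size |
|---|---|---|---|---|---|
| 0% | no choice | 0.40 | −17.4 | −17.4 | 0 |
| 10% | 60% v 40% | 0.42 | −18.1 | −17.4 | 0.7 removed |
| 30% | 80% v 40% | 0.52 | −21.4 | −17.3 | 4.1 removed |
| 50% | 80% v 40% | 0.60 | −24.1 | −17.2 | 6.9 removed |
| 30% | 30% v 40% | 0.37 | −16.4 | −17.4 | 1.0 added |
| 50% | 0% v 40% | 0.20 | −10.7 | −17.6 | 6.9 added |

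The third row, by hand: 0.30 × 0.40 × 0.3446 = 0.041. Moving the intercept from 0 to 2 keeps that row's change between 3.2 and 4.1 points.

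**Second set of assumptions.** Casual sales are about 73 to 74%, 50% of casual visits are served by the stricter type, the seller odds ratio is 2 to 4, the direct attire odds ratio is 0.25 to 0.5, f is 10 to 50% and d is 10 to 40 points. The part carried through the seller is f·d times the seller gap in the uniform arm.
- f = 0.3, d = 0.2, seller OR 2, direct OR 0.5: 0.06 × (0.6796 − 0.5147) = 0.0099, out of a total of 0.7444 − 0.5873 = 0.157, or 6.3%.
- f = 0.5, d = 0.4, seller OR 4, direct OR 0.5: 0.20 × (0.7500 − 0.4286) = 0.0643, out of 0.7286 − 0.5250 = 0.204, or 32%.
- Over the whole grid: 0.16 to 6.55 points, or 0.5% to 32% of the total effect.

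**Scale.** With no shift in who serves and a direct odds ratio of 0.50, the unadjusted odds ratio is still 0.509 (seller OR 2) or 0.535 (seller OR 4), because odds ratios are non-collapsible. The comparison above therefore uses risk differences.

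**The case against.** The strongest reply is that this concerns a contingency in a supporting analysis. Four parts of it deserve an answer.

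- **Status.** The chi-square test is named first and does not condition on the seller, so the randomised contrast is reported whatever the logistic model contains. This stands. A reader might infer that the primary result itself is compromised; the documents do not support that. Nor does the SAP state that every listed covariate enters the model, although no other list exists and none is excluded.
- **Scope.** Recording a variable after the visit does not make it a consequence of attire. With one person on duty, sex and true age are fixed beforehand. The script speaks of a single seller, and one answer to item 14 is that the seller is not in the store, which suggests without proving that one seller is usual. This stands, and it confines the point to multi-seller stores, handovers and error in the age guess. Age error unrelated to arm would only weaken the adjustment.
- **An existing check.** SAP 2.3.1 would show a large shift in seller characteristics. With 1,080/2 = 540 stores per arm and clustering ignored, 52% v 40% is 0.12/√(0.52·0.48/540 + 0.40·0.60/540) = 0.12/0.030, about 4 standard errors; 42% v 40% is about 0.7. This stands in part: the comparison would reveal a large shift. It cannot separate a real handover from arm-dependent guessing, and a difference could be mistaken for chance imbalance and adjusted away.
- **Direction.** Nothing shows that uniforms draw a stricter seller. If they draw a laxer one, adjustment enlarges the apparent effect. This stands, so a claim that adjustment must dilute the effect would go too far.

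A missing-data reading would also be wrong: items 19 and 20 come before the exit at item 23 for buyers asked to leave.

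**Conclusion.** The point holds in a limited form. As written, the SAP lets the adjusted models condition on a variable that, in multi-seller stores, is settled after exposure. In those stores the adjusted estimate can lose or gain part of the attire effect. The range of 0 to about 7 percentage points, in either direction, rests entirely on the assumed share of multi-seller stores, shift in who serves, and difference between sellers. The calculation models one binary seller trait standing in for age; seller sex was not modelled separately. It also assumes that nothing else links who serves to whether a sale is made.

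A gap between the adjusted and unadjusted odds ratios would not by itself show that the problem occurred. The sample size of about 1,080 and the chi-square test are unchanged. The change is still worth making before database lock, because it is cheap and keeps the adjusted estimate on the randomised comparison.

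**What to change.** In SAP 2.3.2 to 2.3.4, name the covariates of the main adjusted models and restrict them to listed variables fixed before the seller sees the buyer: buyer sex and age, store location, region and advertising. The displayed licence, age-of-sale sign and health warning are physical store features. This argument gives no reason to drop them.

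Report seller sex and perceived age descriptively by arm, as SAP 2.3.1 already plans, and include them only in a model labelled supplementary. State there that the seller may be affected by attire.

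The cost is SAP wording and a slight loss of whatever precision the two covariates would have added. No data collection or sample size changes.

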## 2.3. Statistical Methods

### 2.3.1. General Considerations

Summary statistics will be presented for both the treatment and control groups. Continuous variables will be summarized by the number of observations, mean, standard deviation, median, minimum, and maximum. Categorical variables will be summarized using frequency counts and percentages. Descriptive analyses of the distributions of the e-cigarette seller behavior outcomes between two types of attire (treatment and control groups), including successful purchases, inquiring about buyer age, requesting ID cards for age verification, and dissuading buyers from use, as well as store environment features, and sellers' demographic characteristics, will be conducted with t-tests and chi-square tests detecting statistically significant differences.

The significance level for comparisons between the two groups is set at  $\alpha=0.05$  (two-sided). Differences between the study groups will be considered statistically significant if the p-value is less than 0.05. All analyses will be performed using Stata MP 17.

### 2.3.2. Analysis of Primary Outcome

For the primary outcome, successful purchase rates will be analyzed using Chi-square tests to determine if the differences between the treatment group and the control group are statistically significant. Multivariate logistic regression models will be further employed to analyze the treatment effect, adjusting for covariates.

A national map depicting the geographic variations in the outcomes of successful purchase rates will be created using the R package DrawChinaMap.

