7.1.3. Randomization

Prior to the randomization of subjects, all the eligibility criteria must be met.

- **Generating clusters to which the stores belong:** Considering traveling time and the efficiency of data collection, this trial will use a cluster randomization approach, rather than simple randomization. Investigators will firstly map all the 40 selected stores within each metropolitan area, then divide them into clusters that contains the same number (usually 4 stores) considering their locations and public transportation. Then each cluster will be digitally labeled, from area 1 to area 8. The labeling of the clusters follows the principle of from top to bottom, from left to right on the map.
- **Assigning clusters to treatment:** Each cluster will be randomly assigned to one simulated buyer, and the attire (school uniforms or casual attire) he/she wears on a specific day will also be random. In this way, the e-cigarette stores will finally be allocated at a 1:1 ratio to either the intervention or control group.
 - (1) Specifically, the simulated buyers (data collectors) to be recruited are 18 to 19 years old, with a 1:1 ratio of males to females. To reduce bias associated with personal characteristics of simulated buyers, they will be randomly assigned a new digital number for each metropolitan area, which is used for matching the clusters.
 - (2) The type of attire wore by each adolescent on a specific day will be pre-determined using the Excel's random number generator within each sex, and each adolescent will have an equal probability to wear school uniforms and casual attire during the entire study.

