### 1.1.2. Randomization

**Generating clusters to which the stores belong:** Considering traveling time and the efficiency of data collection, this trial will use a cluster randomization approach rather than simple randomization. Investigators will first map all the 40 selected stores within each metropolitan area and then divide them into clusters containing the same number of e-cigarette stores (approximately 5 stores per cluster), taking into account their locations and public transportation. Each cluster will then be digitally labeled, from area 1 to area 8. The labeling of the clusters will follow the principle of from top to bottom, and from left to right on the map.

**Assigning clusters to treatment and control groups:** Each cluster will be randomly assigned to one simulated buyer, and the type of attire (school uniforms or casual attire) they wear on a specific day will also be randomized. In this way, the e-cigarette stores will ultimately be allocated at a 1:1 ratio to either the intervention or control group.

- Specifically, the simulated buyers (data collectors) to be recruited are 18 to 19 years old, with a 1:1 ratio of males to females. To reduce bias associated with the personal characteristics of the simulated buyers, they will be randomly assigned a new digital number for each metropolitan area, which will be used for matching the clusters.
- The type of attire worn by each adolescent on a specific day will be pre-determined using Excel's random number generator within each sex, ensuring that each

adolescent has an equal probability of wearing school uniforms and casual attire during the entire study.

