### **1.4. Sample Size**

Successful purchase rates of e-cigarette products for the school uniform group and casual attire group will be derived from the pilot study. Other parameters required for cluster-RCT sample size calculation are as follows:

- Randomization in a 1:1 ratio for the school uniform (intervention) group and casual attire (control) group
- $\alpha = 0.05$  (two-sided)
- power = 0.85
- cluster size = 4 (both for intervention group and control group)

- inter-cluster correlation coefficient = 0.5 (default)

However, considering the primary goal of this study is to characterize e-cigarette seller behaviors at a national level, we decide to set the final sample size to be approximately 1,080. This may be far more than the minimum sample required (about three times) for testing the effect of buyer attire on e-cigarette sales to adolescents in China.

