### 2.3.3. Analysis of Secondary Outcome

Secondary outcomes, including inquiring about the buyer's age, requesting ID

cards for age verification, and dissuading buyers from use, will be analyzed in a similar manner to the primary outcome. Chi-square tests will be used to detect the statistical significance of differences between the two study groups, and logistic regression models, adjusted for covariates and appropriate for the distribution of the outcomes, will be employed. Additionally, similar national maps describing geographic variations will be generated.

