#### **2.3.4. Analysis of Other Outcomes**

Other outcomes, including illegal flavored products, online contact, and delivery service offered, will be analyzed in a similar way as the primary outcome. Chi-square tests will be used to detect statistical significance in differences between the two groups, and logistic regression models appropriate for the distribution of the binary outcomes with covariate adjustments will be employed. Similar national maps describing geographic variations will be generated as well. For marketing claims and strategies, we will further employ thematic framework analysis to qualitatively analyze and describe the marketing methods and tactics of e-cigarette stores.

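### Attire is randomised by buyer-day cluster, but every attire test treats stores as independent, so the stated 5% level is not controlled

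*SAP*

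**What the plan says.** SAP section 1.1.2 states that "this trial will use a cluster randomization approach rather than simple randomization". Stores in each city are grouped by location, each group goes to one buyer, and that buyer's attire for the day is drawn at random within sex. Protocol section 7.1.3 describes the same scheme and adds that "each adolescent will have an equal probability to wear school uniforms and casual attire during the entire study". Both documents give an overall 1:1 allocation; neither states that attire is balanced within each city.

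SAP section 1.4 (and Protocol section 8.6) sizes the trial as a cluster trial: cluster size 4, power 0.85, two-sided alpha 0.05, and "inter-cluster correlation coefficient = 0.5 (default". It then sets about 1,080 stores, described as about three times the minimum for the attire test.

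For the primary outcome, SAP section 2.3.2 says "successful purchase rates will be analyzed using Chi-square tests to determine if the differences between the treatment group and the control group" are significant, with logistic regression adjusting for covariates. Protocol section 8.2 agrees. The secondary outcomes "will be analyzed in a similar manner to the primary outcome" (section 2.3.3) and the other outcomes "will be analyzed in a similar way as the primary outcome" (section 2.3.4). The decision rule in section 2.3.1 is "Differences between the study groups will be considered statistically significant if the p-value is less than 0.05". The covariates in section 2.2.2 are "Buyer characteristics: Sex, Age", plus seller sex and age and store features that include region.

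**The concern.** Stores visited by the same buyer, on the same day, in the same attire and neighbourhood are likely to give correlated outcomes. An ordinary chi-square test, or logistic regression with model-based standard errors, counts each store as a separate randomised unit. If the correlation is positive and does not cancel between arms, the standard error is too small, confidence intervals are too narrow, and a p-value below 0.05 does not carry a 5% false-positive risk. The plan uses the correlation to set the sample size and then drops it from inference.

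The margin in sample size does not repair this. More clusters raise power, but the design effect depends on cluster size and correlation, not on the number of clusters. Smaller attire effects are most exposed, as are the three secondary outcomes (asking age, requesting ID, dissuading use) and the three other binary outcomes (flavoured products, online contact, delivery).

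**Working it through.** **Inputs from the documents.** Cluster size m = 4, correlation (ICC) 0.5, alpha 0.05 two-sided, power 0.85, N about 1,080 (SAP 1.4). No purchase rates are given; they were to come from the pilot. The planned N therefore cannot be reproduced, and any rate below is an assumption.

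**Formulas.** Design effect DE = 1 + (m − 1) × ICC. True level of the unadjusted test = 2 × (1 − Φ(1.96/√DE)). Unadjusted p needed for a true 0.05 = 2 × (1 − Φ(1.96 × √DE)).

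| ICC (m = 4) | DE | Effective stores (1,080/DE) | True level |
|---|---|---|---|
| 0.05 (assumed) | 1.15 | 939 | 6.8% |
| 0.10 (assumed) | 1.30 | 831 | 8.6% |
| 0.20 (assumed) | 1.60 | 675 | 12.1% |
| 0.50 (plan) | 2.50 | 432 | 21.5% |

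At ICC 0.5 the standard error should be √2.5 = 1.58 times larger, and the chi-square p would have to be below 0.0019 to mean 0.05. At ICC 0.10 the threshold is 0.025.

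**Cluster size.** SAP 1.1.2 gives about 5 stores per cluster because it counts the 8 backups (40/8). The stores to be visited give 32/8 = 4. With m = 5, DE at ICC 0.5 is 3.0 and the level 25.8%.

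**Planned-size effect.** If 1,080 is three times the minimum for 85% power, the cluster-corrected z at that effect is √3 × (1.96 + 1.04) = 5.2, which remains clearly significant.

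**Balance within city.** If each city had exactly equal numbers of uniform and casual buyer-days, city differences would cancel. With s the share of the correlation due to city, DE = 1 + (4(1 − s) − 1) × ICC. This equals 1 at s = 75%: below that the chi-square is inflated, above it conservative. At ICC 0.5 and s = 50%, DE = 1.5 and the level is about 11%.

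**Simulation with no attire effect.** The layout was 36 cities × 8 buyer-days × 4 stores, purchase rate 60% (assumed), 2,500 runs per scenario. The correlation was all buyer-day, or 80% city, or 30% city plus 30% recurring buyer. The three chi-square figures in each cell follow that order.

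| ICC | Independent attire draws | Balanced within city and sex |
|---|---|---|
| 0.1 | 9.8 / 8.3 / 7.9% | 8.8 / 5.0 / 6.6% |
| 0.2 | 11.8 / 10.7 / 11.6% | 12.9 / 5.1 / 9.3% |
| 0.5 | 21.6 / 21.9 / 21.1% | 22.4 / 4.6 / 16.8% |

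Across all 18 scenarios, regression of the buyer-day proportion on attire with city indicators rejected 4.5–6.0%. Logistic regression with city indicators and standard errors clustered on buyer-day rejected 5.9–7.4%.

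A second simulation used 3–4 stores per buyer-day, about 1,080 stores, and rates of 30%, 60% and 85%. The chi-square rejected 6.7–7.0%, 8.1–8.9%, 11.2–12.2% and 20.1–21.0% at ICC 0.05, 0.1, 0.2 and 0.5. The buyer-day regression rejected 4.7–5.3%.

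**The case against.** The best counter-argument is that the size of the problem is unknown and may be small. The ICC of 0.5 is labelled a default; at 0.05 the level is 6.8%, and at 0.01 it is 5.4%. Attire is drawn for a specific day within sex, and a team works in one city at a time, so a reader could infer rough balance within city. With exact balance and 80% of the correlation due to city, the chi-square held 4.6–5.1%. Buyers wear both attires over the study, so some buyer effects cancel. Region is a planned covariate and can absorb some geographic correlation. The planned logistic model without clustering was not simulated, so the percentages above apply to the chi-square.

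Much of this stands as a limit on magnitude. It does not rescue the plan. Exact balance within city is not stated, and even with it the level at ICC 0.5 was 16.8% when buyer and city effects were mixed and 22.4% when the correlation was all buyer-day. Region does not model correlation among stores visited by one buyer on one day. Logistic regression with ordinary standard errors makes the same independence assumption as the chi-square. The phrase in SAP 2.3.3 about suiting the model to the outcome distribution concerns that distribution, not correlation.

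**Conclusion.** The concern holds. The plan randomises clusters, sizes for clusters and then tests as if stores were randomised singly; no section of either document supplies a cluster-aware method. At the plan's own inputs the nominal 5% test has a true level of about 21.5%. That is the upper end of a range, because 0.5 is a placeholder; at assumed ICCs of 0.05 to 0.20 the level is 6.8% to 12.1%. These figures assume m = 4 and no cancellation through balance within city. With exact balance the test could be inflated or conservative, depending on how much of the correlation lies between cities. Either way, the 5% level rests on features that the plan does not specify. A primary effect of the planned size is not in doubt; smaller effects, the six other binary outcomes and all the confidence intervals are. This should be corrected before the analysis is run.

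**What to change.** Prespecify one primary test of attire: linear regression of the buyer-day purchase proportion on attire with city indicators, using a t test with degrees of freedom equal to the number of buyer-days minus 37, and report the risk difference. State how buyer-days with unequal store numbers are weighted. A sex term (sex is the stated randomisation stratum) is a reasonable addition. GEE or a mixed model would also serve; what matters is that one cluster-aware test is named in advance. Then:

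- Use the same test for the secondary and other binary outcomes.
- Keep the logistic models as the covariate-adjusted analysis, with standard errors clustered on buyer-day. At 5.9–7.4% in simulation, they should support the primary test rather than decide it.
- Add a sensitivity analysis clustered on buyer (about 25) with a small-sample correction, because buyers recur across cities.
- Report the observed ICC.
- Keep the chi-square as a descriptive summary. McNemar's test can stay, since it pairs stores visited by the same buyer.

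The cost is SAP wording and a few lines of Stata. The e-cigarette attire analysis needs no new data: date, buyer, city, store ID and attire are on the form in Protocol Appendix 4. Intervals will be wider and nominal power lower. At assumed purchase rates of 60% and 50%, rejection falls from 80% to 51% at ICC 0.5 (where the chi-square's true level is about 21%) and from 88% to 78% at ICC 0.10. About 5 points of that loss come from the city indicators when attire is not balanced within city and there is no city effect: a plain buyer-day t test gave 57% and 83%, against 53% and 78% with the indicators in the same simulation. The indicators are worth keeping if city differences are real.
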